7.0 STUDY PARAMETERS

198 dyads will be recruited, 66 in each of 3 conditions to yield approximately 180 dyads at 8-month analysis.

They will be allowed to keep the phone, so that they could continue to use those interventions if they had other ways to access the two systems. Partners in the A-CHESS group will not have access to either app.

8.0 STATISTICAL CONSIDERATIONS

Data Analysis Plan. The analysis will: 1) explore differences among the three arms over the 8-month active intervention phase and then the 4-month follow-up phase of the RCT; 2) explore the conceptual model (see Figure 3) that considers the relations between the primary and secondary outcomes, and drinker and partner mediators, moderators, and covariates; and 3) examine how the dyad's demographic characteristics (e.g. young drinker and older partner) affect intensity and length of ACHESS-C and FamCHESS-C use and SDT mediators of relatedness, motivation, and competence on study outcomes.

Assumptions and randomization effect. We will report descriptive statistics for all demographic and clinical variables in both arms to ensure that randomization produced comparable groups; if not, variables with significant differences will be included as covariates in a sensitivity analysis. Sensitivity analyses (with and without covariate adjustment) will determine the robustness of covariate-related error control. All outcome variables will be examined using standard summary statistics, visualizations, and tests for normality and homoscedasticity. Data will be transformed for continuous outcomes that do not meet the assumptions of a normally distributed outcome.

Effects of study arm on primary and secondary outcomes (Aim 2). Linear mixed effects models (LMEM)—which account for dependence among successive observations on the same drinker and can address incomplete data—will be used to examine effects of study arm (FamCHESS-C vs. ACHESS-C vs. control, a between-subjects factor) on drinker outcomes over time. We will conduct specific treatment X time contrasts both between and within groups to test time-based effects. For binary, count, and other non-normal data, generalized linear mixed effects models will be used.

Mediation of effects of study arm on primary outcomes (Aim 3). Structural equation modeling (SEM) will explore the effects of mediation on the relation between study arms and our two primary outcomes. We anticipate that the impact of study arm on drinker heavy drinking days and dyad quality of life will be mediated by SDT (competence, relatedness, and motivation) and by drinker's interim change in percent alcohol and drug use days. SEMs involving app use will be run separately for only the ACHESS-C and FamCHESS-C arms.

Moderation of study arm on primary outcome (Aim 3). We will test whether the four variables listed in Figure 3 moderate the effects of the intervention on outcomes. The moderators will be entered as interaction terms in the models described above for the primary outcomes, testing each moderator separately. We will conduct exploratory analyses on whether these moderation effects are also observed for secondary outcomes.

Power. Our primary outcome used to power the study is reduction in percent of heavy drinking days. In our prior study of ACHESS with drinkers coming out of inpatient treatment for AUD, we found an effect size of ACHESS vs. usual care of d=.31 for this outcome.¹⁰⁰ Since then, ACHESS has been improved, and in the proposed study we will incorporate COVID-related content to help drinkers cope with pandemic stresses. Given this, we expect an effect size of d=.40 for the comparison of smartphone control vs. ACHESS-C.

We powered the analysis to be able to detect an effect size of d=.40 for smartphone control vs. ACHESS-C, and then the same magnitude of effect for ACHESS-C vs. FamCHESS-C. It is reasonable to expect an effect of roughly d=.80 for FamCHESS-C vs. smartphone control, given the strong effects observed in an RCT of ABCT, where the effect size for reductions in percent risky drinking days was d=.79.¹⁰¹

We ran the power analyses two ways, based on two different estimates of likely attrition. In prior ABCT and ACHESS studies, 10–21% attrition at 9 and 8 months, respectively, was observed. ¹⁰¹ As the analyses below indicate, an initial sample of 198 dyads would give us adequate power at either rate of attrition.

Starting with a sample of 198, 10% attrition would mean a sample size at 8 months of 180. Across 10,000 LMEM simulations, with post-attrition N=180, we would have power >90% to detect the study arm X time interaction. Starting with a sample of 198, 21% attrition would mean a sample size at 8 months of 159. Across 10,000 LMEM simulations, with post-attrition N=159, we would have power >85% to detect the study arm X time interaction. We will recruit 198 dyads.

Qualitative Analyses (Aim 4). Transcripts of qualitative interviews concerning perceived difficulties and benefits of app use will be examined using Braun and Clarke's¹⁰² six-phase procedure for thematic analysis: 1) familiarization with data, 2) generation of initial codes, 3) identifying instances of themes, 4) review of themes, 5) defining and naming themes, 6) production of findings. To improve consistency and accuracy, coders will work separately using NVivo software; findings will be compared and discussed until consensus is reached.

Interim Analyses and Stopping Plan. The interim analyses are solely to check whether the stopping plan needs to be implemented. They will not be reported as tests of our hypotheses and thus will not inflate Type 1 error. We will engage in the following practices: 1) We will report any fatalities as they occur, as required by the university IRB. 2) Our statistician will conduct interim analyses at months 18 and 27 after the start of the study (9 and 18 months after recruiting begins), examining our primary outcome of substance use days in the two arms. She will share the results with UW's independent Data Safety and Monitoring Board but not with the Pls unless instructed to do so by the Board. Because all of our prior research has been designated low-risk by

the IRB, we anticipate the same designation in this case. Barring exceptional disparities in outcomes between conditions, we do not anticipate stopping the trial. As an *a priori* rule, we believe we should stop if our primary outcome of functional health shows a T-score difference greater than 6 (averaged across components of the PROMIS-29). A T-score of 6 is at the very upper end of the clinically meaningful differences for PROMIS-29 components (e.g. physical function, pain, fatigue).^{22,30} We have no reason to anticipate such an occurrence. We will follow Data Safety Monitoring Board guidance on this matter.

Missing Data. In previous RCTs, we completed about 85% of interviews through 12 months and kept missing data on core interview items to about 2%. We expect these rates in this study. We will identify missing data patterns and use pattern-mixture modeling to test the sensitivity of our analysis to missing data assumptions.¹⁰³⁻¹⁰⁶ We will conduct other sensitivity analyses after imputing missing data with a range of plausible values based on assumptions for the missing data (e.g. best-case, worst-case; with and without multiple imputation).¹⁰⁷⁻¹⁰⁹

Intention-to-Treat and Subject Noncompliance. Standard intention-to-treat (ITT) estimates the average treatment effect by comparing outcomes based on assignment of the treatment, but ignoring use of the treatment. Because ITT effect estimates do not represent treatment efficacy under noncompliance (e.g. a drinker is randomized to FamCHESS-C but does not use the system), we will also estimate noncompliance by estimating treatment effects only for compliers, using As-treated, Per-Protocol¹¹⁰ and CACE.¹¹¹

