Minority recruitment. We will strive to recruit communities of color as they have been disproportionately affected. At the same time, we understand the challenges of minority recruiting and retention. We partner with UW's Collaborative Center for Health Equity and the UW Community Advisors on Research Design and Strategies (CARDS) program to engage and recruit minority groups, including African American and Latinx. Ambassadors from the Collaborative Center facilitate community–academic partnerships and provide culturally tailored training for recruitment and retention. CARDS advisors offer detailed feedback (e.g. on study materials) from a range of racial, socioeconomic, and educational perspectives. We will use CARDS's recruitment and refusal rates. This toolkit includes the National Initiative for Minority Involvement in Clinical Trials website.

Randomization. We will use urn randomization80 after baseline interviews to stratify on drinker's sex, balancing on alcohol use severity (risky drinker, mild, moderate, severe AUD).

Blinding. We will work with the institutional review board (IRB) to blind participants as much as possible to their study arm while maintaining compatibility with guidelines for informed consent. Because all participants receive a phone with some recovery/support-related content, it should be possible to use the same scripts in describing the study arms and expectations for participation. Research staff conducting telephone surveys will be blind to participant condition and study hypotheses, and even when asking about perceptions of the intervention will use standardized questions that apply to any arm (e.g., "How do you feel about the recovery- and support-related content on the phone?"). Data entry will be performed by staff blind to condition.

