Baseline relationship	Dyad	Smartphone data	N/A	0	0, 4 , 8, 12
satisfaction	-			_	
MEASURE	WHO	SOURCE	REFERENCE	# QUEST	TIME (MONTH)
Covariates					
Age	Drinker & partner			1	0
Education	Drinker & partner			1	0
Race/ethnicity	Drinker & partner			2	0

Psychiatric treatment history	Drinker & partner	Question (PhenX tier 1)	Collins et al.87	1	0, 4, 8, 12
COVID acute & residual symptoms	Drinker & partner	Acute and Persistent Symptoms: COVID-19	Carfi et al.99	17	0, 4, 8, 12
Sex	Partner			1	0

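### Covariates for the adjusted sensitivity analysis are chosen by baseline significance rather than prognostic strength, so the robustness check can miss imbalances that matter and adjust for noise

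*Combined protocol and SAP*

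**What the plan says.** The rule is in section 8.0, under Assumptions and randomization effect. All demographic and clinical variables are summarised "in both arms to ensure that randomization produced comparable groups", and "if not, variables with significant differences will be included as covariates in a sensitivity analysis". The next sentence adds: "Sensitivity analyses (with and without covariate adjustment) will determine the robustness of covariate-related error control". No significance level, form of test or list of variables is given. The wording refers to two arms, but the trial has three.

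Other parts of the plan bear on this:

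- The Aim 2 paragraph of section 8.0 says that linear mixed models "will be used to examine effects of study arm (FamCHESS-C vs. ACHESS-C vs. control, a between-subjects factor) on drinker outcomes over time". It names arm and time but no baseline covariate or balancing factor.
- Table 2 in section 6.0 has a Covariates block: age, education, race/ethnicity, psychiatric treatment history and COVID symptoms for both members of the dyad, plus partner sex. Section 8.0 mentions covariates when it describes exploring the conceptual model, but nothing enters this block in the Aim 2 model.
- Section 4.0 (Randomization) uses an urn scheme that stratifies on the drinker's sex and balances alcohol use severity. In section 8.0 these two variables appear only as moderators, each tested separately as an interaction.

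The significance screen is therefore the only rule in the plan for choosing adjustment covariates.

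**The concern.** After randomisation, baseline differences arise by chance, so a test of them answers no open question. How far an imbalance disturbs an estimated arm effect depends on the size of the imbalance and on how well the variable predicts the outcome. The test looks only at the first, and judges it against a threshold set by sample size. A moderate imbalance in a strong predictor can pass unnoticed, while a variable unrelated to drinking or quality of life can be selected.

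What is at stake is the analysis that is meant to show robustness to covariates. Under this rule its content is unknown until baseline data are seen. If nothing is flagged, there may be no adjusted model at all. If something is flagged, agreement with the main result may reassure more than it should.

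**Working it through.** **Inputs from the plan.** 198 dyads in three equal arms (section 7.0), so 198/3 = 66 per arm. Planned effect d=.40 for control vs. ACHESS-C, and the same for ACHESS-C vs. FamCHESS-C (section 8.0, Power). Table 2 covariates: 5 variables × 2 members + partner sex = 11.

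**Assumptions, because the plan gives no figure.** Two-sided alpha .05 for the baseline comparison; independent covariates; covariate-outcome correlation (rho) of .3 to .5, with .7 as a high value.

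**The plan's own figures.** The covariate rule has none. The sample-size figures reproduce approximately: 198 × .90 = 178.2 (plan: 180) and 198 × .79 = 156.4 (plan: 159). With arm means 0/.40/.80 SD, an omnibus F test has power .98 at 180 and .96 at 159, consistent with the stated >90% and >85%.

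**Step 1: what goes unflagged.** Largest non-significant pairwise imbalance = 1.96 × sqrt(2/66) = 0.341 SD. For a binary variable near 50% it is 1.96 × sqrt(2 × .25/66) = 0.171, about 17 percentage points. With one three-arm F test (critical value about 3.04) and the third arm midway, two arms can differ by sqrt(4 × 3.04/66) = 0.43 SD unflagged, so 0.34 is not the least favourable reading.

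**Step 2: worst-case shift in a level contrast** (rho × imbalance).
- rho .3: .3 × .341 = .102 SD; .102/.40 = 26%
- rho .5: .5 × .341 = .171 SD; .171/.40 = 43%

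**Step 3: typical shift.** Median absolute imbalance = .6745 × sqrt(2/66) = 0.117 SD.
- rho .3: .035 SD; 9% of .40
- rho .5: .059 SD; 15% of .40

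**Step 4: chance selection.** P(at least one flagged) = 1 − .95^11 = .43, with 11 × .05 = .55 variables expected. With 20 variables it is 1 − .95^20 = .64. With 11, nothing is flagged in 1 − .43 = 57% of trials.

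**Step 5: simulation.** 10,000 trials per scenario; 66 per arm; one prognostic and ten irrelevant covariates; three-arm F screen at .05; ACHESS-C vs. control at a single follow-up. This simplifies the planned mixed model, so its power values should not be set against the plan's >90%.
- The prognostic covariate was flagged in about 5% of trials. When the rule selected anything, about 88% of the time it selected only irrelevant variables.
- About 21–22% of trials had an unflagged imbalance of at least 0.2 SD in the prognostic covariate. In those trials the rule-based estimate was off by .13 SD on average (rho .5) or .19 SD (rho .7), and false rejection under the null was 7.8% or 12.5%.
- Over all trials, null rejection under the rule was .044 (rho .5) and .042 (rho .7).
- Prespecifying the prognostic covariate, at d=.40, raised power from .63 to .75 (rho .5) or from .64 to .89 (rho .7). The SD of the estimate fell from .167 to .149, or from .168 to .125.

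**The case against.** The strongest reply is that the rule touches only a sensitivity analysis. That stands. A reader might infer that the primary result is biased or that the trial's type I error is inflated; the documents do not support either. The Aim 2 mixed model is not selected by this rule, chance imbalance is already reflected in its standard error, and overall null rejection under the rule stays below .05. The 7.8% and 12.5% are conditional on a particular kind of trial.

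A reader might also take 26–43% as the expected distortion. It is the edge case: the largest imbalance that escapes the screen, multiplied by assumed correlations. It also concerns outcome level, whereas the plan tests arm-by-time contrasts and collects the outcome at month 0. A covariate that predicts baseline and follow-up equally shifts such a contrast by about zero; what counts is its association with change.

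Other points stand in part:

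- The urn scheme protects drinker sex and severity, so exposure lies mainly in other predictors.
- Drinker and partner characteristics are probably correlated, which would lower the 43%.
- Adding an irrelevant covariate costs degrees of freedom but does not bias a randomised comparison.
- The sentence on analyses with and without adjustment could be read as allowing a wider adjusted analysis. It names no covariates, so it does not replace the screen.

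It would go too far to call the check uninterpretable. It is less informative than it could be.

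**Conclusion.** The point holds as a weakness of the sensitivity analysis that should be corrected; it does not threaten the primary analysis. The screen leaves pairwise imbalances up to 0.34 SD unflagged and has a 43% probability of flagging something by chance among 11 covariates, given alpha .05 and independence. The consequence for a level contrast is about 9–15% of d=.40 for a typical imbalance and 26–43% at worst, at assumed correlations of .3 to .5. It is smaller for arm-by-time contrasts to the extent that the covariate predicts baseline and follow-up equally. The rule also gives up precision that a fixed set of prognostic covariates would provide. The Table 2 list does not settle the matter: it is tied to no Aim 2 model, and its Covariates block omits drinker sex, alcohol severity and the month-0 outcome, which are the randomisation factors and probably the strongest predictors.

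**What to change.** Delete the significance screen. Prespecify one adjusted sensitivity analysis for each primary outcome, fitted whatever the observed balance, containing:

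- drinker sex and alcohol use severity, as the urn factors;
- the month-0 value of the outcome, either as a covariate with later months as responses or as part of the response series, but not both;
- a short list of Table 2 covariates chosen now on prognostic grounds, using month-0 values only (some are measured repeatedly), with partner covariates added for dyad outcomes;
- covariate-by-time terms where the contrast is arm by time.

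Present descriptive baseline tables for all three arms and correct the two-arm wording. The cost is SAP wording and a few degrees of freedom. No new data are needed, and the change should be made before outcome data are examined by arm.

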Data collection. Surveys will be conducted with both members of the dyad in all three study arms every 4 months (baseline, 4, 8, and 12 months). Each participant receives \$25 per completed survey. Payments will be processed in 2 ways. If the participant prefers to receive the payment in the mail, we will send cash to the participant within 5 business days of their survey being completed. If the participant prefers to receive payment through a mobile app, we will send them payment through Venmo or Paypal.

UW staff blind to the hypotheses will conduct the surveys. To ensure fidelity and data quality, we will record interviews, and [name] will review a subset and provide feedback. All uses of the apps are automatically logged to create measures of use of different services. Survey data will be double-entered into ICTR REDCap and compared to reduce the chance of data-entry errors. Both survey and app data are stored on a UW Division of Information Technology HIPAA-secure server using the Campus Computing Infrastructure. The timing of interviews will be based on enrollment date.

Once the trial begins, we will analyze app use data every 2 weeks to note trends in services used most and differences in use patterns between drinkers and partners. One tool for drinkers in ACHESS-C and FamCHESS-C will be a weekly survey adapted from the Brief Alcohol Monitor (BAM),81 with four COVID-related protective behavior questions added. Our adaptation of the BAM asks about 5 factors that put patients at risk of relapse and 5 factors that protect. Responses help CHESS systems tailor services to individual patients and partners. We will also add questions to the every-4-months interviews. Some app-based questions will change over time as we explore specific issues. For instance, if a service is not used for a month, we will add a question about why. If certain services are used a great deal, we will ask how and why it's useful, to understand if additional related resources are needed.

Keeping patients and partners engaged. Other CHESS studies have increased engagement in 4 ways. We will use all: 1) Monitor and respond to changes in the amount of app use. 2) Examine discussion posts using tools we developed that are based on Linguistic Inquiry and Word Count74 and machine learning82-84 to

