6.0 MEASUREMENT OF EFFECT

Variables reflect the conceptual model (see Figure 3, above) and study aims. Measures chosen have good psychometric properties with similar populations. Where possible, we used PhenX and PROMIS measures (e.g. PROMIS 29.2) so that results are comparable to other studies.⁸⁵ Our primary outcome is percent days of heavy drinking, but given 2015 FDA draft guidelines we also include number of patients with *no* heavy drinking days per period as a secondary outcome.⁸⁶ Table 2 lists our measures, number of questions, and sources, with references to validation studies where relevant. In the R34, we collected much of the same data we propose to collect in the RCT. Survey completion time averaged about 90 minutes.

Table 2: Proposed Measures, Scales, and Sources for Study Outcomes and Other	
Variables	

MEASURE	WHO	SOURCE	REFERENCE	# QUEST	TIME (MONTH)
		Primary Outcomes			
% days heavy drinking	Drinker	Timeline Follow Back ⁸⁷	Johnston et al. ⁸⁸	7	0, 4 , 8, 12
Quality of life	Dyad	PROMIS 29.2	Hamilton et al.85	29	0, 4, 8, 12
		Secondary Outcomes			
Relationship satisfaction	Dyad	OQ-45.2 ⁸⁹	Beckstead et al.89	45	0, 4 , 8, 12
Physical/psychological conflict	Dyad	Rev. Conflict Tactics	Straus et al.90	20	0, 4 , 8, 12
No heavy drinking days	Drinker	Timeline Follow Back ⁸⁷	Johnston et al. ⁸⁸	7	0, 4 , 8, 12
% days alcohol or drug use	Drinker	Timeline Follow Back ⁸⁷	Johnston et al. ⁸⁸	7	12
COVID vaccination completion	Dyad			1	0, 4 , 8, 12
Drinking/drug problems	Drinker	Clinical evaluation guide	Spitzer et al.91	5	0, 4 , 8, 12
	Ē	Exploratory outcomes			
Crisis healthcare use (ER, 30 day readmits)	Dyad	Treatment Services Reviews	McCollister & French ⁹²	3	0, 4 , 8, 12
% days alcohol or drug use	Partner	TLFB last 60 day	Collins et al. ⁸⁷	11	0, 4 , 8, 12
Satisfaction with technology	Dyad	Tech Accept Model93	Szajna ⁹⁴	26	4, 8, 12
		Mediators			
Competence	Dyad	CCQ / # of skills used	Schroder & Ollis ⁹⁵	11	0, 4 , 8, 12
Relatedness	Dyad	Revised Important People	Zwiak et al.96	14	0, 4 , 8, 12
Motivation	Dyad	Brief Self Control Scale	Tangney et al.97	13	0, 4 , 8, 12
Reductions over 8 months % days alcohol or drug use	Drinker	Timeline Follow Back ⁸⁷	Johnston et al. ⁸⁸	7	0, 4 , 8
For ACHESS-C vs. FamCHESS-C: use of app	Dyad	Smartphone data	N/A	0	0, 4 , 8, 12
		Moderators			
Sex	Drinker			1	0
Concurrent treatment services	Drinker	TSR	McLellan et al.98	10	0, 4 , 8, 12
Severity baseline alcohol	Drinker	Smartphone data	N/A	0	0, 4 , 8, 12

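### The Aim 2 mixed model does not say how the pre-randomisation baseline enters; one common baseline mean would sharpen the arm contrasts using data already collected (precision only, no bias)

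*Combined protocol and SAP*

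**What the plan says.** Section 8.0, under the effects of study arm (Aim 2), specifies linear mixed models for drinker outcomes over time, with arm as a between-subjects factor, and adds: "We will conduct specific treatment X time contrasts both between and within groups to test time-based effects". Binary, count and other non-normal outcomes go to generalised linear mixed models. No sentence says whether the baseline value is a response, a covariate, or a mean held equal across arms.

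The Power paragraph of the same section says "Our primary outcome used to power the study is reduction in percent of heavy drinking days". It states power above 90% (N=180) and above 85% (N=159) for the arm-by-time interaction, with d=.40 for each of the two adjacent comparisons.

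Section 4.0 assigns arms by "urn randomization80 after baseline interviews", stratifying on drinker's sex and balancing on a four-level alcohol severity class. Section 5.0 surveys all arms at months 0, 4, 8 and 12. Baseline is therefore one of four visits and precedes assignment.

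Sex and severity appear in the analysis only as Aim 3 moderators, entered as interaction terms one at a time. Covariate adjustment is confined to a secondary step: "variables with significant differences will be included as covariates in a sensitivity analysis".

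**The concern.** Because baseline precedes randomisation, any month-0 difference between arms is chance. A model that estimates three baseline means and then subtracts them carries that chance difference into the treatment contrast. A model with one baseline mean does not, and it uses the correlation between baseline and follow-up more efficiently.

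The stake is the two adjacent contrasts that Hypothesis 1 needs: ACHESS-C against control, and FamCHESS-C against ACHESS-C, each assumed at d=.40. These have far less power than FamCHESS-C against control (d about .80) or a three-arm omnibus test.

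Two smaller matters go with this. The factors that drive the urn are not adjustment terms in the model. And choosing sensitivity covariates by significance of baseline differences tracks chance imbalance, not prognostic value.

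**Working it through.** **Inputs from the documents.** 198 dyads, 66 per arm; 180 (60 per arm) or 159 (53 per arm) at month 8; d=.40 per adjacent contrast; visits at 0, 4, 8 and 12 months.

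**Assumed, because not given.** Two-sided alpha .05; baseline to month-8 correlation ρ of .3 to .8; compound symmetry; equal SDs at all visits (varied in step 4); d on the outcome SD; time as a factor.

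**1. The plan's own figures.** 198 × .90 = 178 and 198 × .79 = 156, close to the stated 180 and 159. The stated power cannot be pinned down without alpha, ρ, the SD scale and the exact contrast. With complete data at month 8 and d in SDs of change, the omnibus 2-df test (means 0/.40/.80) gives 98.0% at N=180 and 96.3% at N=159. A single d=.40 contrast gives 59.1% and 53.9%.

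**2. Formula, complete data.** With n per arm and SD 1, the pairwise contrast variance is

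- free baseline means (change): (2/n) × 2(1−ρ)
- one common baseline mean: (2/n) × (1−ρ²)
- ratio: (1+ρ)/2

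At ρ=.5, n=60, the variances are 2/60 = .0333 (SE .183) and 2 × .75/60 = .025 (SE .158). Power is Φ(.40/SE − 1.96): 59.1% and 71.6%.

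**3. With the plan's attrition.** Four-visit generalised least squares with known covariance, 66 per arm at baseline, dropout split equally after months 0 and 4:

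| ρ | Variance ratio, 60 per arm | Power, free to common | Variance ratio, 53 per arm | Power, free to common |
|---|---|---|---|---|
| .3 | .671 | 47 to 63% | .697 | 44 to 58% |
| .5 | .766 | 60 to 72% | .787 | 56 to 67% |
| .7 | .861 | 82 to 87% | .874 | 78 to 83% |
| .75 | .884 | 88 to 91% | .895 | 85 to 88% |
| .80 | .907 | 94 to 96% | .916 | 91 to 93% |

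An AR(1) pattern with the same baseline to month-8 correlation moves the ratios by at most .004. If d is on the change SD instead, power at 60 per arm goes from 61 to 78% (ρ=.3), 60 to 72% (.5) and 60 to 67% (.7).

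Omnibus test at 60 per arm: 92.7 to 98.8% (ρ=.3) and 98.3 to 99.7% (ρ=.5). At 53 per arm: 90.4 to 97.7% and 97.2 to 99.3%.

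**4. Unequal SDs.** Let s be baseline SD divided by follow-up SD. With complete data the ratio is (1−ρ²)/(1+s²−2ρs). The denominator equals (1−ρ²)+(s−ρ)², so the ratio never exceeds 1 and reaches 1 when s=ρ. At ρ=.5 and s=.8 this is .75/.84 = .893. With the 10% attrition pattern:

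- ρ=.5: .593 (s=1.25), .766 (s=1), .901 (s=.8), .954 (s=.7), 1.000 (s=.5)
- ρ=.7: .861 (s=1), .982 (s=.8), 1.000 (s=.7)
- ρ=.3: .671 (s=1), .800 (s=.8)

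**5. Urn factors.** Simulation of 2,500 trials: 60 per arm, four complete visits, ρ=.5, common baseline, SE of the month-8 contrast:

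| Variance explained by the factors | No factors | Main effects | With time interactions |
|---|---|---|---|
| 20% at every visit | .160 | .154 | .155 |
| 30% at baseline, 5% later | .159 | .163 | .159 |

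Main effects alone range from a 4% gain (.154/.160 = .96) to a 2.5% loss (.163/.159 = 1.025). With time interactions the range is a 3% gain (.155/.160 = .97) to no change. These are two scenarios, not bounds.

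**The case against.** The strongest reply is that no error is shown. The text would also describe a common-baseline model, which has arm-by-time effects too. The free-baseline comparator is the natural reading, not stated text. If the authors already intend baseline adjustment, most of the gain is already there and only wording is missing. That stands, and is why this is offered as an improvement.

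Second, the 8 to 33% range depends on equal baseline and follow-up SDs. That also stands: step 4 shows that the gain can vanish or be larger.

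Third, judged against the plan's own power claims the gain is modest. If they are pairwise (month-8 contrast, time as a factor), the table needs ρ of about .75 to .80, where the gain is 2 to 4 points. If they refer to the omnibus test, it already has about 90% power or more at ρ of .3 and above. That stands.

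Two stronger readings are tempting and are not supported. A reader might infer that the treatment estimate is biased; with randomisation after baseline, the change contrast is unbiased. A reader might also infer that the plan would adjust for post-randomisation values, because Table 2 lists covariates such as "Acute and Persistent Symptoms: COVID-19" at months 0, 4, 8 and 12. Those are collection times. The screen in Section 8.0 asks whether randomisation gave comparable groups, which points to baseline variables.

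**Conclusion.** The point holds as a free gain in precision. With known covariance, a common baseline mean is never less precise than a free-baseline change contrast, and it needs no new data. Under equal SDs, compound symmetry and the plan's attrition, the month-8 pairwise variance falls by 8 to 33% for ρ from .8 to .3. The gain shrinks to nil as baseline SD falls towards ρ times follow-up SD, and grows if baseline SD exceeds follow-up SD. It falls mainly on the two adjacent d=.40 contrasts; the omnibus test gains little unless ρ is low.

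The urn factors add little after that. Their main merit is that the analysis then matches the randomisation. The significance screen is a lesser matter, since it does not touch the primary estimate.

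The figures are for percent heavy drinking days treated as continuous. They do not apply to outcomes analysed by generalised mixed models, and were not computed for dyad quality of life, the other primary outcome.

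**What to change.** In the Aim 2 paragraph of Section 8.0:

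1. For continuous outcomes in the linear mixed model, fit months 0, 4, 8 and 12 with one common baseline mean across arms and arm-by-time effects at months 4, 8 and 12.
2. Prespecify drinker sex and the severity class recorded for the urn as covariates, each with its time interactions. Main effects alone lost precision in one of the two scenarios above.
3. For the covariate sensitivity analysis, replace the significance screen with a fixed list of baseline variables.

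The cost is SAP wording. One baseline mean replaces three. Sex (1) and severity (3) add 4 parameters, or 4 + 4 × 3 = 16 with time interactions, against 198 dyads at four visits. No new data are needed: the baseline survey and the urn already supply every value.
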